Eligible patients will be given a letter containing instructions for the eligible family and/or household members on how to be referred for the initial screening visit and information about the importance of CV disease primary prevention (Appendix A). If there has been no contact from an eligible family or household member two weeks following the CV patient's hospital discharge, a member of the healthcare team will contact the CV patient by phone to remind him or her to contact eligible family or household members.

Informed consent for participation in the study will be obtained from the patient at the time of enrolment during index hospitalization and other participants at the time of the initial screening visit. Institutional research ethics approval will be obtained for this study.

Cardiovascular Screening for Family Members of People with Acute Coronary Disease: A Patient-Initiated and Family-Oriented Strategy

PI: [name]

Risk Factor Screening and Treatment

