Participants will have a follow-up visit at 6-months during which they will undergo a history and physical exam and have lipid and glucose blood tests drawn. The Paffenbarger physical activity scale, Food Frequency Questionnaire, and an Information Assessment Method questionnaire (see section A3) will be administered. Interim follow-up appointments (maximum 2 per participant) may be scheduled if needed. At the 6-month visit, participants will receive an individualized report of CV risk factor control and their change in 10-year modified CV risk. Reports will be sent to the primary care physician if applicable. Participants without primary care physicians will be given resources on how to register for one.

The patient with coronary disease and all participating family and household members will be encouraged to attend the initial screening visit and all subsequent healthcare interactions. The history and physical exam will be done without other participants present in order to preserve confidentiality. Patients who accompany their family and household members to the appointments will also be encouraged to take their secondary preventive medications and continue follow-up with their treating physician, since half of patients who have a myocardial infarction stop taking their evidence-based preventative medications within 12 months of the index event.⁷

Cardiovascular Screening for Family Members of People with Acute Coronary Disease: A Patient-Initiated and Family-Oriented Strategy

PI: [name]

Assessment of Participant Comprehension and Engagement in Care

At the 6-month clinic visit, the Information Assessment Method (IAM), a self-administered 1-page questionnaire (Appendix C), will be distributed to participants (patients, family members, and household members). The IAM is will be used to systematically evaluate the (1) acquisition and relevance of new information, (2) practical impact, (3) expected health benefits, and (4) associated barriers or facilitators.^{8, 9} Using a mixed-methods approach, we will review the IAM responses to understand the factors associated with the referral and screening program and to generate recommendations and feedback to the participants. The IAM is considered a knowledge translation tool by the Canadian Institute for Health Research.¹⁰

Data Collection

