A research assistant will be based in the Division of Cardiology at the JGH and will have a dedicated space in the clinical research department with a computer-equipped workstation. The research assistant will be responsible for obtaining informed consent and extracting data from the patient record.

From the patient, we will collect the following data: age, sex, ethnicity, willingness to refer family members and reasoning, whether CV screening was done prior to hospitalization, CV risk factors (including family history of CV disease), description of the acute coronary event, cardiac unit and hospital length of stay, and approximate number of eligible family or household members.

From the family or household members, we will collect the following data: age, sex, gender, ethnicity, relationship with CV patient, whether the patient has a primary care physician and last time seen, CV symptoms on history, medications, weight, BP Tru recording, physical examination findings, physical activity, nutrition, and other CV risk factors identified (i.e., obstructive sleep apnea). Baseline and 6-month CV individual risk factor values will be recorded (i.e., blood pressure, lipid levels, HbA1c), as well as baseline and 6-month modified Framingham 10-year risk scores. A 30-year Framingham risk score will be recorded at baseline and 6-months for patients who are under age 30 at the time of study enrolment. Results from the IAM, nutrition, and physical activity at the 6-month visit will also be collected.

Measures

The effectiveness of the screening strategy will be measured by the total number of participants identified at intermediate or high risk on the modified Framingham CV risk score (>10% risk of a CV event over the following 10-year period). The effectiveness of the primary prevention intervention will be measured by the change in percentage of the mean modified Framingham 10-year CV risk score for family and household members between the initial visit and 6-month follow-up. The most recent Canadian Cardiovascular Society guidelines strongly recommend CV risk assessment using the modified Framingham 10-year risk score to guide therapy and to repeat the risk assessment when there is an expected change in risk status.⁴

Cardiovascular Screening for Family Members of People with Acute Coronary Disease: A Patient-Initiated and Family-Oriented Strategy

PI: [name]

Data Analysis

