Results will be stratified by age (<65; \geq 65) and sex. Continuous data will be presented as mean with standard deviation or median with interquartile range and between group differences will be tested with the Student's t test and the Mann-Whitney U test, respectively. Categorical data will be presented as frequencies and percentages and will be compared using the chi-squared test or the Fisher exact test, as appropriate. All p values will be two-sided with values \leq 0.05 indicating statistical significance. Statistical tests will be done using the SPSS 24.0 statistical software (IBM Corp, Armonk, New York). Statistical analysis will be performed by statisticians affiliated with the Lady Davis Institute for Medical Research (Montreal, Quebec).

References

1. Kardia SL, Modell SM and Peyser PA. Family-centered approaches to understanding and preventing coronary heart disease. *American Journal of Preventive Medicine*. 2003;24:143-51.

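### The 6-month change in Framingham risk has no stated within-person estimate or interval, and every test listed in Data Analysis ignores that relatives of one patient may be correlated

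*Combined protocol and SAP*

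**What the plan says.** The Measures section names two effectiveness measures. The screening strategy is judged by the number of participants above 10% risk. The prevention intervention is judged by this quantity: "change in percentage of the mean modified Framingham 10-year CV risk score for family and household members between the initial visit and 6-month follow-up".

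For this second measure, the data are paired. Data Collection records individual risk factor values at both visits, "as well as baseline and 6-month modified Framingham 10-year risk scores". Under Risk Factor Screening and Treatment, at the 6-month visit "participants will receive an individualized report of CV risk factor control and their change in 10-year modified CV risk".

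Data Analysis is one paragraph. "Results will be stratified by age" and sex. Continuous data are summarised as mean and SD or median and IQR, and "between group differences will be tested with the Student's t test and the Mann-Whitney U test, respectively". Categorical data "will be compared using the chi-squared test or the Fisher exact test, as appropriate". On significance, "All p values will be two-sided with values" of at most 0.05 counting as significant. No confidence interval, paired test, signed-rank test or repeated-measures model is named.

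Participants can come in families. Patient Identification and Recruitment requires at least one eligible relative or household member and sets no upper limit. The index patient receives a letter with "instructions for the eligible family and/or household members on how to be referred for the initial screening visit". Risk Factor Screening and Treatment encourages all participating members to attend visits together with the patient.

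**The concern.** One of the two effectiveness measures is a before-after change in the same people, but the analysis section describes only how to compare one set of people with another. It says how to compare men with women. It does not say how to estimate whether risk fell, or with what precision. The estimate, its interval and its scale could then be settled after the data have been seen.

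Families add a second problem. The protocol includes household members because they share habits such as smoking, diet and inactivity, and it encourages relatives to attend together. Changes in risk may therefore be alike within a family. All the listed tests assume independent participants, and so does a plain paired t test. Naming a paired test would close the first gap and leave the second open.

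**Working it through.** **Inputs.** Two-sided alpha of 0.05 comes from Data Analysis, and two scores per participant from Data Collection. The documents give no sample size, SD, power, within-person correlation (rho), number of relatives per index patient (m) or within-family correlation of the change (ICC). There is thus no planned figure to reproduce, and rho, m and ICC below are assumptions shown over a range.

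**1. Which stated method fits which question?**
- Number above 10% risk: a count, which needs none of the tests.
- Differences between age or sex strata: Student's t, Mann-Whitney U, chi-squared or Fisher.
- Change from the initial visit to 6 months in the same people: none. Student's t can name a paired test, but here it governs between-group differences and is coupled with Mann-Whitney U, an independent-samples test.

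**2. A paired t test that ignores families.** With m relatives per patient, the variance of the mean change is multiplied by DE = 1 + (m − 1) × ICC. The actual type I error is 2 × [1 − Φ(1.96/√DE)], and the correct interval is √DE times as wide as the one reported.

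| m | ICC | DE | 1.96/√DE | Type I error | √DE |
|---|---|---|---|---|---|
| 1, or any m with ICC 0 | – | 1.00 | 1.960 | 5.0% | 1.00 |
| 2 | 0.05 | 1.05 | 1.913 | 5.6% | 1.02 |
| 2 | 0.1 | 1.10 | 1.869 | 6.2% | 1.05 |
| 2 | 0.3 | 1.30 | 1.719 | 8.6% | 1.14 |
| 3 | 0.3 | 1.60 | 1.550 | 12.1% | 1.26 |

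A simulation with 40 families, rho 0.5 and 20,000 data sets gave 6.2%, 8.5% and 12.2% for the last three rows. A paired analysis of family means, which respects the families, gave 5.1%, 5.1% and 4.8%.

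**3. The listed tests between strata.** Take m = 2, ICC 0.3 and two equal strata.
- If both relatives fall in the same stratum, the variance of the difference is multiplied by 1 + 0.3 = 1.3. Type I error is 2 × [1 − Φ(1.96/√1.3)] = 8.6%.
- If each pair is split across strata, it is multiplied by 1 − 0.3 = 0.7. Type I error is 2 × [1 − Φ(1.96/√0.7)] = 2 × [1 − Φ(2.343)] = 1.9%.

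A mixture of the two lies between these values.

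**4. If the two-sample tests were applied to the two visits.** With equal SDs, the ratio of the SE used to the true SE is 1/√[(1 − rho) × DE]. Without clustering this is 1.20, 1.41 and 2.24 at rho 0.3, 0.5 and 0.8, so the test is conservative. It becomes anti-conservative only when rho is below 1 − 1/DE, for example below 1 − 1/1.3 = 0.23 at m = 2 and ICC 0.3.

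**5. Scale.** A change in percentage of a mean that is itself a percentage can be read in two ways. An illustrative fall from 12% to 10% is 2 percentage points, or 2/12 = 16.7% relative to baseline.

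**The case against.** The strongest reply is that this is an omission and not a wrong method. Data Analysis never says that the listed tests will be applied to the two visits, no hypothesis about the change is stated, and the 0.05 threshold governs only such p values as are produced. Reporting the mean change descriptively would comply with the text. The analysis is assigned to statisticians, and each participant's own change is already calculated for the 6-month report.

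Much of this stands. A reader might infer that the plan will compare the visits with an unpaired test and lose most of its power. The documents do not support that: on the natural reading the groups are the age and sex strata, so step 4 is a conditional remark and not the size of the problem. Nor do they show that the method will be chosen after the data are seen, only that nothing prevents it. It is also fair that families may cause little or no inflation: one relative per patient satisfies the entry criteria, and nothing in the documents supports an ICC as high as 0.3 for a change score.

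The reply does not remove the gap. A measure said to show effectiveness needs a statement of precision, and naming who will analyse the data does not name the method. Nor does reading the groups as strata make the listed tests sound, because those comparisons also take relatives as independent.

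**Conclusion.** The point holds as an omission joined to an independence assumption that the design makes doubtful. The change in Framingham risk has no stated within-person estimate or interval, its scale is ambiguous, and no listed test allows for relatives of the same index patient. No other section supplies what is missing.

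The omission can be read directly from the text. Its numerical size cannot. The 5.0% to 12.1% range for a paired test and the 8.6% or 1.9% for comparisons between strata depend on assumed family sizes and correlations. A reader might take 12.1% as the study's false-positive rate; it is only the upper end of the range shown. The count of participants above 10% risk is not affected. The gap should be closed before the data are analysed.

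**What to change.** In Data Analysis, state that the effectiveness of the prevention intervention is the mean of each participant's 6-month minus baseline modified Framingham score, in percentage points, with a 95% CI and p value from a paired analysis with standard errors clustered by index patient. Relative change may be reported as secondary. Then:

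- Use the same clustering for comparisons between age and sex strata, and for any before-after comparison of blood pressure, lipids or HbA1c that is reported.
- Record an index-patient identifier for each relative. Data Collection lists the relationship to the patient but no linking identifier.
- Report how many participants have no 6-month score, and their baseline scores.

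The cost is a short paragraph, one data item and a little more analysis work; both scores are already collected. Intervals may be somewhat wider than those that ignore families, by the √DE factors in the table. Participants without a 6-month score do not contribute to the paired estimate, which is why their number and baseline scores must be shown.

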Cardiovascular Screening for Family Members of People with Acute Coronary Disease: A Patient-Initiated and Family-Oriented Strategy

PI: [name]

Study Protocol

Patient Identification and Recruitment

The prospective study will be conducted at the Jewish General Hospital (JGH), an academic tertiary care referral centre in Montreal, Quebec. The JGH's acute care cardiovascular unit has 16 beds equipped for advanced hemodynamic and ventilator support and 32 ward beds with continuous telemetry. An outpatient cardiology clinic is adjacent to the inpatient unit.

Patients admitted to the JGH over a 12-month period will be assessed for eligibility into the study by a member of the research team. Inclusion criteria are patient age ≤ 70 years old admitted with an initial diagnosis of an acute coronary event, such as acute coronary syndrome or myocardial infarction, and at least 1 first-degree family or household member age ≥ 18 years old. Exclusion criteria are no eligible family or household members, inability to contact family or household members, distance to study centre too far as determined by the patient, or family or household members who have been screened for CV disease in the previous 2 years. Family or household members with known coronary disease will also be excluded.

Household members of the patient will be included in the study. There is evidence that partners and other non-genetically related household members, who do not have the same hereditary predisposition as the patient with CV disease, share social and lifestyle influences such as smoking habits, low physical activity, and diet, and have higher rates of CV disease than would be expected.¹

Younger relatives (≥ 18 years old) of the CV patient will be included as well. Younger relatives (typically under age 30) have been excluded from most prior screening studies.² The optimal screening and management strategy for younger relatives of CAD patients is unclear. Early risk factor assessment and counselling of younger patients may promote lifelong changes in lifestyle choices and behaviours with long-term benefits.³

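### Student's equal-variance t test is named for comparing age and sex strata that the design does not make equal in size or spread; naming Welch's version would protect the stated 5% level

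*Combined protocol and SAP*

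**What the plan says.** The protocol's Data Analysis section opens with "Results will be stratified by age", using 65 years as the cut, and by sex. Continuous variables are to be summarised either by means and SDs or by medians and IQRs. For comparing groups, the tests matched to these two summaries are "Student's t test and the Mann-Whitney U test, respectively". The error level is set by a sentence beginning "All p values will be two-sided with values", with 0.05 or below counted as significant. The software is SPSS 24.0.

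The section names no unequal-variance test and no check of equal variances. It plans no confidence intervals. It does not say outright that the groups being tested are the age and sex strata. The study has no control arm, however, and the section offers no other grouping, so that is the natural reading.

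On who enters, Patient Identification and Recruitment states "Inclusion criteria are patient age ≤ 70 years old". Relatives and household members are admitted from age 18 with no upper limit, and those with known coronary disease or recent cardiovascular screening are excluded. No sample size, stratum size or SD appears anywhere.

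**The concern.** In ordinary usage, Student's two-sample t test estimates one pooled variance and applies it to both groups. That does no harm when the groups are of equal size, or when their spreads are equal. When both size and spread differ, the pooled standard error is wrong. It is too small if the smaller group has the larger variance, and too large if the larger group has it.

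A fixed age cut and a split by sex leave the stratum sizes to chance. For age there is some reason to expect trouble. The index patient is at most 70, and children of the patient are much younger. The exclusions for known disease and recent screening plausibly remove older people more often. The main continuous measure is a 10-year risk percentage bounded at zero, so young adults may cluster near the floor while older adults spread out. A smaller, more variable stratum aged 65 and over would be the case that gives too many false positives. This is inference, not something the documents show. They give no comparable argument for sex.

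What is at stake is whether a p value of 0.05 or below in a stratum comparison means what the plan says it means.

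**Working it through.** The plan states no figure to reproduce. The error level (0.05, two-sided) and the choice of test come from Data Analysis. All stratum sizes and SD ratios below are assumptions.

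**Formulas.** With sizes n1, n2 and SDs s1, s2:

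- pooled variance: sp² = [(n1−1)s1² + (n2−1)s2²] / (n1+n2−2)
- squared standard error used by Student's test: sp²(1/n1 + 1/n2)
- true squared standard error: s1²/n1 + s2²/n2
- R = square root of (used / true)
- approximate error rate: 2[1 − Φ(1.96 × R)]

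**Smaller stratum more variable, 80 against 20.**

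- SD ratio 1.5: sp² = (79×1 + 19×2.25)/98 = 1.242; used = 1.242 × 0.0625 = 0.0776; true = 1/80 + 2.25/20 = 0.125; R = 0.788; error rate about 12%.
- SD ratio 2: sp² = (79×1 + 19×4)/98 = 1.582; used = 0.0989; true = 1/80 + 4/20 = 0.2125; R = 0.682; error rate about 18%.

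**Larger stratum more variable, 80 against 20.**

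- SD ratio 1.5: sp² = (79×2.25 + 19×1)/98 = 2.008; used = 0.1255; true = 2.25/80 + 1/20 = 0.0781; R = 1.267; error rate about 1.3%.
- SD ratio 2: sp² = (79×4 + 19×1)/98 = 3.418; used = 0.2136; true = 4/80 + 1/20 = 0.100; R = 1.462; error rate about 0.4%.

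**Simulation** (normal data, 40,000 replicates per setting). The two Student columns each give SD ratio 1.5, then 2.

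| Split | Student, smaller stratum more variable | Student, larger stratum more variable |
|---|---|---|
| 80:20 | 12.1%, 18.1% | 1.4%, 0.4% |
| 160:40 | 11.9%, 17.9% | 1.4%, 0.4% |
| 90:10 | 15.7%, 25.0% | 0.8%, 0.1% |
| 60:40 | 7.0%, 8.4% | 3.4%, 2.9% |

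At 50:50 Student's test gave 5.0% to 5.2%. With equal SDs it gave 4.9% to 5.2% at every split. Welch's test gave 4.9% to 5.2% in every setting. Doubling the total from 100 to 200 at the same 4:1 split hardly changes the result, so a larger study does not cure the problem.

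**Price of Welch's test if the SDs are in fact equal** (simulated power, target near 80%, Student then Welch): 50:50, 78.9% and 78.9%; 60:40, 79.3% and 79.2% (rounded); 160:40, 79.7% and 78.9%; 80:20, 79.0% and 77.2%; 90:10, 79.1% and 72.2%.

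**Skewed data.** With gamma-distributed data, splits of 160:40, 170:30 and 80:20, the smaller stratum more variable and SD ratios of 1.5 and 2, Welch's error rate was about 5% to 6% at skewness 1, 6% to 8% at skewness 2, and 7% to 10% at skewness 2.8. Student's was about 12% to 22%.

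**The case against.** The strongest reply is that the direction is unknown. Without stratum sizes or SDs, Student's test could be too liberal, too strict or about right. Relatives have no upper age limit, so partners and parents of index patients could fill the older stratum. This stands. A reader might infer that the plan's p values will be too small; the documents do not support that for age, and they offer nothing either way for sex. But an open direction is a reason to choose a test that holds its level in both cases.

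Three further readings go too far.

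- That confidence intervals would be too narrow: none are planned.
- That Mann-Whitney is a faulty fallback because effectiveness is defined through a mean: the mean measure under Measures is a within-person change from first visit to 6 months, not a contrast between strata. A rank test for data shown as medians is a legitimate choice.
- That Welch's test is free and exact: it loses some power at very unequal splits if the SDs are equal, and it is only approximate under strong skew.

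It is also fair to say that if older people are more variable because their mean risk is higher, the null hypothesis for the score itself is false and a false-positive rate does not apply to it. The error rates bear on continuous variables whose stratum means may truly be equal, such as possibly the change in score, for which no variance is documented. For the score itself, what remains is a miscalibrated standard error.

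Finally, the plan does not write out the pooled form, nor equate the groups with the strata. Both are reasonable readings rather than explicit statements.

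**Conclusion.** The point holds as a minor one. Data Analysis names a test that assumes equal variances for groups whose sizes and spreads the design does not control, and gives no alternative. If sizes and SDs both differ, the stated 5% level is missed. At an assumed 80:20 split with an SD ratio of 1.5 to 2, the actual level lies at about 12% to 18% or about 0.4% to 1.4%, depending on which stratum is more variable. At 60:40 the departure is small, and at equal sizes negligible. Which case applies cannot be settled from the documents.

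The conclusion is limited to comparisons of means between strata. It does not bear on the within-person change in risk score or on the count of participants above 10% risk.

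**What to change.** In Data Analysis, replace Student's t test with the Welch (unequal-variance) t test for between-stratum comparisons of means, and state that the groups compared are the age and sex strata. Keep Mann-Whitney for data shown as medians.

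This is a change of one line, best made before the data are seen, and standard software reports the unequal-variance result beside the pooled one. The statistical cost is the power loss shown above if the SDs turn out equal: about 1 to 2 points at 4:1 and about 7 at 90:10. For strongly skewed variables Welch's p value should be read as approximate.

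### Every p value at or below 0.05 counts as significant, across all outcomes and by age and sex, and no test is set apart for the effectiveness claim

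*Combined protocol and SAP*

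**What the plan says.** Data Analysis is a single paragraph. Its decision rule begins "All p values will be two-sided with values" and sets the bar at or below "0.05 indicating statistical significance". Its scope is broad: "Results will be stratified by age (<65" against 65 and over, and also by sex, with no outcome named. For continuous data, "between group differences will be tested with the" t test or the Mann-Whitney U test. Categorical data "will be compared using the chi-squared test or the Fisher exact test, as appropriate". None of these tests is tied to an outcome. The section has no primary test, ordering, multiplicity rule or statement that any analysis is exploratory.

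Measures names one yardstick per aim. For screening: "The effectiveness of the screening strategy will be measured by the total number of participants identified at intermediate or high risk". For the intervention: "The effectiveness of the primary prevention intervention will be measured by the change in percentage of the mean modified Framingham 10-year CV risk score", taken in family and household members from the initial visit to 6 months. Neither is called primary, and neither is given a hypothesis or a test.

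Data Collection adds other quantities: "Baseline and 6-month CV individual risk factor values will be recorded (i.e., blood pressure, lipid levels, HbA1c"), together with weight, physical activity, nutrition and the Information Assessment Method responses.

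**The concern.** A 0.05 threshold limits the error of one test. Applied to every test in a set, it does not limit the chance that at least one of them produces a false claim. Under the rule as written, a p value of 0.04 for nutrition by sex is significant on the same terms as a p value of 0.04 for the change in 10-year risk. Emphasis could then be chosen after the data are seen. A chance difference in one risk factor or one age group could be presented as a result of the programme, while the measure the protocol chose for effectiveness has no protected place in the analysis.

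**Working it through.** **The plan's own figure.** The only error rate in the documents is 0.05 per test. For one test, 1 - (1 - 0.05)^1 = 0.05, so the figure is right for one test and no more. There is no stated sample size, power or overall error rate to reproduce.

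**Inputs.**
- Threshold: 0.05, two-sided, for all p values (Data Analysis).
- Stratifiers: 2, age and sex (Data Analysis).
- Number of quantities compared: not given, so this is an assumption. Eight can be listed from Measures and Data Collection: blood pressure, lipids, HbA1c, weight, physical activity, nutrition, 10-year score, and number above 10% risk. Four is used as a low count, in case only some are tested.
- Correlation between outcomes: not given. Varied from 0 to 0.7.
- All null hypotheses true: an assumption.

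**Independent tests.** The chance of at least one false positive in k tests is 1 - 0.95^k.
- 4 quantities x 2 stratifiers, k = 8: 1 - 0.95^8 = 0.337.
- 8 quantities x 2 stratifiers, k = 16: 1 - 0.95^16 = 0.560.

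The expected number of false positives is 0.05k: 0.4 for k = 8 and 0.8 for k = 16. Correlation does not change these expectations.

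**Correlated tests.** The outcomes are measured in the same people, so independence overstates the chance of at least one false positive. A simulation of 200,000 runs per row used equally correlated normal test statistics within each stratifier, independent stratifiers, and a two-sided 0.05 cut-off:

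| Correlation | 4 x 2 tests | 6 x 2 tests | 8 x 2 tests |
|---|---|---|---|
| 0 | 33.5% | 46.0% | 55.9% |
| 0.3 | 31.8% | 42.4% | 51.3% |
| 0.5 | 28.7% | 37.2% | 44.0% |
| 0.7 | 24.4% | 30.2% | 34.5% |

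The zero-correlation row agrees with the formula. The range is about 24% to 56%, which is 5 to 11 times the stated 5% (24.4/5 = 4.9; 55.9/5 = 11.2).

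**If some differences are real.** A true age or sex difference that reaches significance is not a false positive. Suppose the four comparisons on the 10-year score and the count derived from it (2 quantities x 2 stratifiers) are real. Then 16 - 4 = 12 true nulls remain, and 1 - 0.95^12 = 0.460 if independent.

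**The case against.** The strongest reply is that this is a single-centre before-after study whose plan is largely descriptive, and that Measures already ranks the outcomes. Only two Framingham-based quantities are described as measuring effectiveness. The individual risk factors appear only as data to be collected, and age and sex only as stratifiers. A reader might infer that the plan has no ordering of outcomes at all. That goes too far: the ordering exists in Measures. What stands against the plan is that Data Analysis does not carry it into the tests. It attaches significance to all p values and labels nothing exploratory. A study presented as descriptive would not need full multiplicity adjustment, but this plan does not say that it is descriptive.

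A second reply concerns the calculation. The number of tests is assumed, the assumption that every null is true is doubtful, and two of the eight quantities are the same score, once continuous and once cut at 10%. All of this is fair. It is why the result is given as a range and not as a single figure.

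A third reply is that naming one test is not enough. Data Analysis lists only comparisons between separate groups, whereas the intervention measure is a change within the same people. Several participants may also be relatives of one patient. This stands, and the fix has to deal with it.

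**Conclusion.** The point holds as a gap in the decision rule, and it should be corrected. As written, the plan allows any secondary or subgroup result to be claimed as significant at an overall error rate that nobody has set. The chance of at least one false positive is about 24% to 56%, assuming 4 to 8 quantities by two stratifiers, correlations from 0 to 0.7, and all nulls true. Real differences would lower it; more tests than assumed would raise it.

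Two stronger readings are not supported. A reader might infer that a false claim is more likely than not. Most of the scenarios above fall below one half, the plan never lists its tests, and it does not describe which results will be reported. A reader might also double the 16 tests to 32 for two visits and arrive at 1 - 0.95^32 = 0.806. The plan does not say that tests are run separately at each visit. Weight is listed without a 6-month value, and no repeat count of participants above 10% risk is planned. Repeat readings in the same people are also not independent.

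**What to change.** Amend Data Analysis in three respects.

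1. Reserve the two-sided 0.05 significance claim for one test: the change in modified Framingham 10-year risk from the initial visit to 6 months in family and household members.
2. Specify that test as a paired, within-person change, with standard errors that allow for clustering by index patient. Record a link from each participant to the index patient so that this can be done.
3. State that all other results are exploratory and will be reported as estimates with 95% confidence intervals and no significance claim. This covers screening yield, individual risk factors, questionnaires, and every age and sex comparison.

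With one valid confirmatory test, the overall error rate for the significance claim is 0.05. The cost is a few sentences, slightly more analysis work for the clustered paired analysis, and fewer secondary results that can be called significant. No extra visits or measurements are needed.
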